- Any concomitant medications/products/vaccines relevant to an SAE/Adverse Event of Special Interest (AESI) to be reported as per protocol or administered at any time during the study period for the treatment of an SAE/AESI's. In addition, concomitant medications relevant to SAEs and AESI's need to be recorded on the Expedited Adverse Event report.

7.5.2. Concomitant medications/products/vaccines that may lead to the elimination of a subject from per-protocol analyses

The use of the following concomitant medications/products/vaccines will not require withdrawal of the subject from the study but may determine a subject's evaluability in the per-protocol analysis. See section 10.2 for populations to be analysed.

- Any investigational or non-registered product (drug or vaccine) other than the study vaccine used during the study period.
- Long-acting immune-modifying drugs administered at any time during the study period (e.g. infliximab).
- Any anti-CD20 or other B-cell monoclonal antibody agents (e.g., rituximab, ocrelizumab) used at any time during the study period.
- A vaccine against HZ (including an investigational or non-registered vaccine) other than the study vaccine during the study period.
- A live vaccine administered during the period starting 30 days before the first revaccination dose and ending 30 days after the last revaccination dose*.
- An inactivated/subunit vaccine, including influenza vaccine, administered during the period starting 8 days before the first revaccination dose and ending 30 days after each revaccination*.

*In case an emergency mass vaccination for an unforeseen public health threat (e.g., a pandemic) is organized by the public health authorities, outside the routine immunization program, the time period described above can be reduced if necessary for that vaccine provided it is licensed and used according to its Summary of Product Characteristics (SmPC) or PI and according to the local governmental recommendations and provided a written approval of the Sponsor is obtained.

- Immunoglobulins and/or any blood products administered during the period starting 90 days before any scheduled visit.
- Drug and/or alcohol abuse.

A detailed, comprehensive list of reasons for elimination from per-protocol analyses will be established prior to data cleaning.

CONFIDENTIAL212340 (ZOSTER-073 EXT:041 Y4-10)
Protocol Amendment 1 Final

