4.4. CCI	
4.5. Other Safety Analyses	39
4.5.1. Extent of Exposure	40
4.5.2. Adverse Events.....	40
4.5.3. Additional Safety Assessments.....	40
4.6. Other Analyses	42
4.6.1. Subgroup analyses	42
4.6.2. Sensitivity Analyses	43
4.7. Interim Analyses	44
4.8. Changes to Protocol Defined Analyses	45
5. SAMPLE SIZE DETERMINATION	45
6. SUPPORTING DOCUMENTATION	45
6.1. Appendix 1 Study Population Analyses.....	45
6.1.1. Subject Disposition	45
6.1.2. Demographic and Baseline Characteristics.....	46
6.1.3. Protocol Deviations	46
6.1.4. Prior and Concomitant Medications and Vaccinations	47
6.1.5. Study Intervention Compliance	47
6.1.6. Additional Analyses Due to the COVID-19 Pandemic	47
6.2. Appendix 2 Data Derivations Rule	47

CONFIDENTIAL

6.2.1.	Baseline Immunogenicity	48
6.2.2.	Assessment Window	48
6.2.3.	Multiple measurements at One Analysis Time Point	48
6.2.4.	Attributing events to vaccine doses.....	49
6.2.5.	Handling of Missing Data	49
6.2.6.	Data Derivations	51
6.2.7.	Display of decimals.....	54
7.	REFERENCES.....	55

Version history

SAP Version	Approval Date	Protocol Version (Date) on which SAP is Based	Change	Rationale
1.0	12 Mar 2024	Amendment 1 Final: 15 June 2020	Not Applicable	Original version
2.0	12 Mar 2024	Amendment 1 Final: 15 June 2020		
			
Section 1.2:
 
 Added immunogenicity summaries where Visit 1, Visit 2, and Visit 3 in the LTFU phase of ZOSTER-073 will also be presented as Day 1, Month 12, and Month 24, 	
 In accordance to the primary endpoint timepoints for public disclosure
			
Section 3.1:
 
 Added PPS(LTFU) as a population that elimination code 2060 is applicable to and clarified the type of elimination is Visit(s) only, as applicable 	
 Concomitant infections could occur in the LTFU phase which could impact immunogenicity assessments at a particular visit or visits
			
Section 4.2:
 
 Clarified the immunogenicity 	
 Clarification that

SAP Version	Approval Date	Protocol Version (Date) on which SAP is Based	Change	Rationale
			summaries of seropositivity rates, GMCs, and MGI of anti-gE antibody in the LTFU phase will not be provided by age and immunosuppressive therapy	summaries will no longer be provided by subgroup

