Code	Condition under which the code is used	Analysis set eliminated from	Visit (timepoints) where the code is applicable	Type of Elimination
	revaccinated without fulfilling the eligibility criteria for revaccination	(revacc. follow-up phase)		
2040	Administration of any concomitant medication(s) forbidden by the protocol	PPS (revacc. active phase), PPS (revacc. follow-up phase)	Visit 1 – Visit 7	Eliminate from Visit(s) only, as applicable
2050	Underlying medical condition forbidden by the protocol, or some Intercurrent medical conditions (IMCs). (To be determined before analysis during data management review (DMR))	PPS (LTFU), PPS (revacc. active phase), PPS (revacc. follow-up phase)	Visit 1 – Visit 7 (visit and onward)	Eliminate from Visit and onwards
2060	Concomitant infection related to the revaccination which may influence immune response – For example, clinically diagnosed suspected HZ cases before Visit 1 or PCR confirmed HZ cases after Visit 1	PPS (LTFU), PPS (revacc. active phase), PPS (revacc. follow-up phase)	Visit 1 – Visit 7	Eliminate from Visit(s) only, as applicable
2070	Concomitant infection not related to the vaccine which may influence immune response – For example, in case of revaccination, any additional confirmed or suspected immunosuppressive or immunodeficient condition (e.g., malignancy, hepatitis, HIV infection, systemic infection)	PPS (LTFU), PPS (revacc. active phase), PPS (revacc. follow-up phase)	Visit 1 – Visit 7	Eliminate from Visit and onwards
2080	Out of window treatment administration – Revaccination dose 1 (study Month 24) to revaccination dose 2 (study Month 25) outside 25-90 day interval	PPS (revacc. active phase), PPS (revacc. follow-up phase)	Visit 3 – Visit 4	Eliminate from Visit and onwards
2090	Missed Visit, excluding phone contact Note: this does not apply to delayed enrolled subjects who had their Visit 1 and Visit 2 on the same day.	PPS (LTFU), PPS (revacc. active phase), PPS (revacc. follow-up phase)	Visit 1 – Visit 7	Eliminate from Visit only
2090	Assessment not properly performed – For example, incomplete assessment, missed assessment except safety follow-up Note: this does not apply to delayed enrolled subjects who had their Visit 1 and Visit 2 on the same day. These subjects would have to have an assessment at either Visit 1 or Visit 2.	PPS (LTFU), PPS (revacc. active phase), PPS (revacc. follow-up phase)	Visit 1 – Visit 7	Eliminate from Visit only

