4.8. Changes to Protocol Defined Analyses

The protocol states the Enrolled Set will be used for analyses of safety and immunogenicity for non-revaccinated subjects, however, the PPS for analysis of persistence (LTFU phase) was amended in this SAP such that it includes Visit 6 (study Month 37) and Visit 7 (study Month 49) for non-revaccinated subjects, therefore, the PPS for analysis of persistence will be used for analyses of immunogenicity and the Enrolled Set will be used for analyses of safety in non-revaccinated subjects.

The protocol states the percentage of subjects reporting at least one SAE related to primary vaccination classified by MedDRA Primary SOC and PT from ZOSTER-041 Day 1 to ZOSTER-073 pre-revaccination will be tabulated with exact 95% CI. Any SAEs related to primary vaccination from ZOSTER-041 Day 1 through the last ZOSTER-041 study visit will be taken from the ZOSTER-041 CSR. Any SAEs that occurred after the last ZOSTER-041 study visit and through ZOSTER-073 pre-revaccination will be captured on the ZOSTER-073 CRFs and summarized according to Section 4.3.2.1.

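### SAP elimination code 2040 omits the LTFU per-protocol set, so several non-vaccine drugs in protocol 7.5.2 have no explicit route out of the primary persistence analysis

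*SAP*

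**What the plan says.** **SAP 3.1.** Code 2040 covers "Administration of any concomitant medication(s) forbidden by the protocol". It applies from Visit 1 to Visit 7, removes only the visits concerned, and acts on two sets: PPS (revaccination active phase) and PPS (revaccination follow-up phase). PPS (LTFU) is not named. The matching code for forbidden vaccines, 1040, does name it.

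**Protocol 7.5.2.** The heading describes products "that may lead to the elimination of a subject from per-protocol analyses", with no restriction to revaccination. The non-vaccine entries include "Any anti-CD20 or other B-cell monoclonal antibody agents (e.g., rituximab, ocrelizumab) used at any time during the study period" and "Immunoglobulins and/or any blood products administered during the period starting 90 days before any scheduled visit". Long-acting immune-modifying drugs at any time in the study, and investigational or non-registered drugs during the study, are also listed. The text says that use may affect evaluability, and that a full list of elimination reasons will be drawn up before data cleaning.

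**Protocol 7.6 and SAP code 2050.** Section 7.6 counts conditions that call for immunoglobulin or blood products as intercurrent medical conditions (IMCs). Code 2050 names PPS (LTFU) and takes some IMCs, to be chosen at DMR. Its stated type removes the visit and all later ones.

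**SAP version history.** Version 2.0 records "Added PPS(LTFU) as a population that elimination code 2060 is applicable to", with the reason "Concomitant infections could occur in the LTFU phase which could impact immunogenicity assessments at a particular visit or visits".

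**The concern.** Anti-gE concentration at Day 1, Month 12 and Month 24 is the first primary endpoint, and SAP 4.2 analyses it on PPS (LTFU). B-cell depletion can lower an antibody level for reasons unrelated to how long the vaccine response lasts; passive antibody can raise it. The 7.5.2 windows reach the LTFU visits, yet no code that acts on PPS (LTFU) is written for drug use. A Visit 1 sample could be removed from a revaccination table and kept in the primary persistence table.

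Exposure is foreseeable. Protocol 8.1.14 mentions intravenous immunoglobulin and anti-B-cell agents in the management of rejection. The enrolment exclusions do not name these products; only the revaccination exclusions do. Subjects barred from revaccination on that ground may stay in follow-up, and SAP section 3 analyses their immunogenicity in PPS (LTFU).

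The rest of the plan does not close the gap. The Enrolled Set analysis contains the same samples, and users who are never coded out do not count toward the 5% trigger for running it. The only sensitivity analysis in SAP 4.6.2 concerns dialysis recipients in the revaccination follow-up phase.

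**Working it through.** **1. Is code 2040 out of line with the rest of the table?** Sorting the SAP 3.1 rows by first applicable visit:

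- Starting at Visit 1: 800 and 900 act on all sets. Codes 1040, 2050, 2060, 2070, 2090 (missed visit; assessment not properly performed), 2100 and 2120 all name PPS (LTFU). Code 2040 does not.
- Omitting PPS (LTFU): 1030, 1070, 1080, 1090, 2010, 2080, the two interval rows of 2090, and 2500 all start at Visit 3 or later. Code 2040 starts at Visit 1.

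Code 2040 is the only row that starts at Visit 1 and leaves PPS (LTFU) out.

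**2. Which entries of 7.5.2 are affected?**

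| Entry in protocol 7.5.2 | Code naming PPS (LTFU) |
|---|---|
| Investigational or non-registered product | Vaccine: 1040. Drug: none |
| Long-acting immune-modifying drug | None |
| Anti-CD20 or other B-cell agent | None |
| Other HZ vaccine | 1040 |
| Live vaccine | 1040 |
| Inactivated or subunit vaccine | 1040 |
| Immunoglobulin or blood product | 2050, if taken as an IMC at DMR |
| Drug or alcohol abuse | None (not a product) |

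**3. Can DMR supply the missing set?** SAP 3.1 lets DMR decide whether a code applies to all visits, one visit, or a visit and those after it. It does not say that DMR may add an analysis set.

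**4. Numbers.** The plan's own figure reproduces: 86 × 0.85 = 73.1, stated as about 73. SAP 1.2 gives actual enrolment as 68; with the same 15% loss, 68 × 0.85 = 57.8, about 58.

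If k of n samples are each multiplied by a factor f, the GMC is multiplied by f^(k/n). The documents give neither k nor f. The values below are assumptions, chosen for B-cell depletion because that class has no explicit route.

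| n | k | f = 1/3 | f = 1/10 | Fall in GMC |
|---|---|---|---|---|
| 68 | 1 | 0.984 | 0.967 | 1.6% to 3.3% |
| 68 | 3 | 0.9527 | 0.9034 | 4.7% to 9.7% |
| 58 | 3 | 0.9448 | 0.8877 | 5.5% to 11.2% |

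The main LTFU tables use yearly intervals, whose row sizes are not given. A row with fewer samples would move more for the same k.

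**5. The 5% trigger.** If all 68 have serology, 0.05 × 68 = 3.4, so four eliminated subjects are needed (4/68 = 5.9%; 3/68 = 4.4%).

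**The case against.** The omission may be deliberate. Immunoglobulin, blood products and B-cell agents appear as exclusions only for revaccination (protocol 6.2.2.2), and 7.5.2 says that their use does not require withdrawal. One can argue that they are forbidden only with respect to revaccination, so code 2040 belongs only to those sets. This reading is coherent, but the SAP does not state it. It also sits badly with the 7.5.2 windows, with code 1040, and with the version 2.0 edit that gave code 2060 the LTFU set.

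The discretionary routes are wider than a first look suggests. Section 7.6 counts any clinical event that might move anti-gE levels as an IMC, so a rejection episode treated with a B-cell agent might be taken under 2050. That stands, but it depends on a judgement about the event and not on a rule about the drug.

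A reader might infer that the SAP departs from the protocol without declaring it. Section 4.8 does list changes, beginning "The protocol states the Enrolled Set will be used for analyses of safety and immunogenicity for non-revaccinated subjects", and code 2040 is not among them. But 7.5.2 is permissive and defers the final list, and SAP 3.1 can be read as supplying that list. Choosing from a permissive list need not be a declared change.

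A reader might also infer that the row contradicts itself by starting at Visit 1. It does not: SAP 1.2 shows the LTFU visits in the revaccination tables.

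**Conclusion.** The gap is real but narrow. Investigational drugs, long-acting immune-modifying drugs and B-cell agents have no explicit elimination route from the set used for a primary analysis. Immunoglobulin and blood products have a route that depends on a choice at DMR. It would be too strong to say that every product in 7.5.2 is stranded, since code 1040 covers vaccines.

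It would also be too strong to say that the primary GMC is biased. Nothing in the documents shows that any LTFU sample is affected. The fall of about 5 to 10% rests on three affected samples out of 68 and a 3- to 10-fold depression, all assumed. Medians and reverse cumulative curves, also planned, would move little, and no hypothesis is tested. The point is worth correcting because it leaves inclusion in a primary analysis to a review-time judgement, or to no explicit rule, when a written rule costs almost nothing.

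**What to change.** 1. Add PPS (LTFU) to code 2040, keep its visit-only type, and cite the non-vaccine products in protocol 7.5.2, so that the word forbidden has a definite list behind it.
2. State that 2040 takes precedence over 2050 when product exposure is the only reason for elimination. Otherwise both codes apply to immunoglobulin with different scopes, one visit against that visit and all later ones.
3. Before database lock, and without reference to the serology results, fix which visits count as affected by long-acting and B-cell agents. Section 7.5.2 gives no window for these, so adding the set alone would leave the choice open.
4. If the omission is intended, say so in the SAP and give the reason.

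An LTFU GMC row with and without the removed samples is optional. It would keep them visible when fewer than four subjects are eliminated and the Enrolled Set analysis is not triggered.

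The cost is one table cell and a few sentences. No new data are needed: protocol 7.5.1 already records these products during the study, and 8.1.3 looks back 90 days (immunoglobulin and blood products) and 360 days (long-acting and B-cell agents) before Visit 1. The downside is that a few samples may leave a small per-protocol set, against the SAP's stated aim of keeping as much LTFU data as it can.

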4. STATISTICAL ANALYSES

4.1. General Considerations

4.1.1. General Methodology

Confidence intervals (CIs) will use 95% confidence levels unless otherwise specified.

The exact confidence intervals around within-group proportions are derived using the method of Clopper and Pearson [[Clopper](#), 1934].

Unless otherwise specified, continuous data will be summarized using descriptive statistics: n, mean, standard deviation (std), median, minimum, and maximum. Categorical data will be summarized as the number and percentage of subjects in each category.

4.1.2. Baseline Definition

For the LTFU phase, baseline is latest non-missing pre-primary series dose assessment from ZOSTER-041 study.

For the revaccination active and follow-up phases, baseline is the latest pre-revaccination dose assessment with a non-missing result from ZOSTER-073.

To assess long-term follow-up duration and decline post primary vaccination series peak-response, 1 month post-dose 2 of primary vaccination in ZOSTER-041 will be used.

Unless otherwise stated, if baseline data is missing, no derivation will be performed, and baseline will be set to missing.

4.2. Primary Endpoints Analyses

The primary immunogenicity analysis for the LTFU phase will be performed using the PPS for analysis of persistence (LTFU phase from Visit 1 to Visit 3 for all subjects, and at Visit 6 and Visit 7 for non-revaccinated subjects). If 5% subjects or more with serological results are eliminated from the PPS for analysis of persistence, then a complementary analysis will be performed on the Enrolled Set.

The primary immunogenicity analysis for the revaccination active phase will be performed on the PPS for immunogenicity after revaccination course (revaccination active phase). If 5% subjects or more with serological results are eliminated from the PPS for revaccination active phase, then a complementary analysis will be performed on the Exposed Set.

All analyses will be performed overall.

4.2.1. Definition of endpoints

GMC calculations will be performed by taking the anti-log of the mean of the log base 10 concentration transformations. The 95% CIs for GMC will be based on a back transformation of the student CI for the mean of the log-transformation. Antibody concentrations below the cut-off of the assay will be given an arbitrary value of half the cut-off for the purpose of GMC calculation. The cut-off for the anti-gE Ab assay is 97 mIU/ml.

The vaccine response rate (VRR) is defined as the percentage of subjects who has at least:

- a 4-fold increase in the post last vaccination anti-gE Ab concentration as compared to the pre-vaccination anti-gE Ab concentration for subjects who are seropositive at baseline.

OR

- a 4-fold increase in the post last vaccination anti-gE Ab concentration as compared to the anti-gE Ab cut-off value for seropositivity for subjects who are seronegative at baseline.

A seropositive subject has an anti-gE Ab concentration is greater than or equal to the cut-off value. The seropositivity rate is defined as the percentage of seropositive subjects.

The mean geometric increase (MGI) of anti-gE antibody concentrations over pre-vaccination in the initial ZOSTER-041 study is defined as the geometric mean of the within subject ratios of the post-vaccination reciprocal anti-gE concentration to the Day 0 reciprocal anti-gE concentration.

The MGI of anti-gE antibody concentrations after revaccination over pre-revaccination is defined as the geometric mean of the within-subject ratios of the post-revaccination reciprocal anti-gE concentration to the Month 24 reciprocal anti-gE concentration.

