10.3.3. Immunogenicity analyses**LTFU phase**

Analyses will be based on the Per Protocol Set (PPS) for persistence after primary vaccination course.

If, the percentage of subjects with serological results excluded from the PPS for analysis of persistence after primary vaccination course is 5% or more, a second analysis based on the Enrolled set will be performed to complement the PPS analysis.

All analyses will be performed overall; additional analyses by age and type of maintenance immunosuppressive therapy strata (at the time of primary vaccination in study ZOSTER-041) will be performed if deemed necessary and appropriate.

CONFIDENTIAL

212340 (ZOSTER-073 EXT:041 Y4-10)

Protocol Amendment 1 Final

Endpoint	Statistical Analyses for LTFU phase
Primary	
For persistence of humoral immunity after the primary vaccination course, the following parameters will be tabulated:
 
 • GMCs of anti-gE antibody and anti-gE antibody seropositivity rates with 95% CI at Day 1, Month 12 and Month 24; • Descriptive statistics on anti-gE antibody concentrations (mean, SD, min, Q1, median, Q3, max) at Day 1, Month 12 and Month 24; • Vaccine response rates to ZOSTER-041 primary vaccination for anti-gE antibody concentrations at ZOSTER-073 Day 1, Month 12 and Month 24; • Descriptive statistics of the fold increase over ZOSTER-041 pre-vaccination timepoint at ZOSTER-073 Day 1, Month 12 and Month 24 (mean, SD, min, Q1, median, Q3, max); • Distribution of the fold over ZOSTER-041 pre-vaccination timepoint at ZOSTER-073 Day 1, Month 12 and Month 24; • MGI, i.e. geometric mean of the ratio post-vaccination timepoint over pre-vaccination timepoint in ZOSTER-041 with 95% CI at ZOSTER-073 Day 1, Month 12 and Month 24; 
The distribution of antibody titers at Day 1, Month 12 and Month 24 will be tabulated and also presented using reverse cumulative curves.

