Primary	
For humoral immunity after revaccination for the active phase, at Months 24, 25 and 26, the following parameters will be tabulated:
 
 • GMCs of anti-gE antibody and anti-gE antibody seropositivity rates with 95% CI at Months 24, 25 and 26; • Vaccine response rates for anti-gE antibody concentrations at Months 25 and 26 [post- revaccination timepoint over pre-revaccination timepoint] with 95% CI; • Vaccine response rates to ZOSTER-041 primary vaccination for anti-gE antibody concentrations at ZOSTER-073 Months 25 and 26 with 95% CI; • MGI post-revaccination timepoint over pre-revaccination timepoint at Months 25 and 26 with 95% CI; • MGI post-revaccination timepoint over ZOSTER-041 pre-vaccination timepoint at Months 24, 25 and 26 with 95% CI; • Descriptive statistics of the fold increase of anti-gE antibody concentrations at Month 25 and Month 26 over pre-revaccination timepoint (mean, SD, min, Q1, median, Q3, max). • Distribution of antibody titers at Months 24, 25 and 26 will be tabulated and also presented using reverse cumulative curves.
Secondary	
For cellular immunity after revaccination for the active phase, the following parameters will be tabulated:
 
 • Descriptive statistics (N, mean, SD, min, Q1, median, Q3, max): 
 – the frequency of gE specific CD4+T-cells secreting at least 2 activation markers (among IFN-γ, IL-2, TNF-α, CD40L) at Months 24, 25 and 26; – the fold increase over pre-revaccination timepoint Month 24 in the frequency of gE specific CD4[2+] T-cells at Months 25 and 26. – the fold increase over ZOSTER-041 pre-vaccination timepoint in the frequency of gE specific CD4[2+] T-cells at Months 24, 25 and 26 in the current study. • Vaccine response rates for frequency of gE-specific CD4(2+) T-cells at Months 25 and 26 over pre-revaccination timepoint Month 24 will be tabulated with 95% CI. • Vaccine response rates to ZOSTER-041 primary vaccination for frequency of gE-specific CD4(2+) T-cells at ZOSTER-073 Months 24, 25 and 26 will be tabulated with 95% CI.

GMC = Geometric Mean Concentration, **MGI** = Mean Geometric Increase, **N** = Number, **SD** = Standard Deviation, **Q1** = Quartile 1, **Q3** = Quartile 3, **Min** = Minimum, **Max** = Maximum, **IFN- γ** = Interferon gamma, **IL-2** = Interleukine 2, **TNF- α** = Tumor Necrosis Factor alpha.

Revaccination follow-up phase

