12.2. Appendix 2: Clinical laboratory tests

12.2.1. Clinical laboratory tests

Specific antibody (anti-gE) measurements

Anti-gE ELISA: Anti-gE Ab concentrations will be measured using an anti-gE ELISA. Diluted blood serum samples of study subjects will be added to microtiter wells pre-coated with VZV gE recombinant antigen. Secondary peroxidase-conjugated anti-human antibodies will be added, which bind to the primary human anti-gE antibodies. After incubation of the microtiter wells with a chromogen substrate solution, the enzymatic reaction will be stopped. Optical densities will be recorded and anti-gE antibody concentrations are calculated from a standard curve. The assay will be performed on human serum at GSK laboratory or another laboratory designated by GSK.

Intracellular cytokine staining

CMI responses will be performed by GSK (or designated laboratory) on thawed PBMCs by ICS. The assay will be performed on samples collected during the course of the study. This assay provides information on the frequency of CD4+ T-cells responding to culture medium or antigens (gE peptide pool) by secreting cytokine molecules involved in immunity such as IFN- γ , IL-2, TNF- α , and CD40L.

Briefly, PBMC collected from the subjects are stimulated for two hours using culture medium (for evaluation of the non-specific response), a pool of overlapping peptides covering the entire sequence of the vaccine antigen gE. Then, an intracellular block (brefeldin A) is added to inhibit cytokine secretion for a subsequent overnight incubation. Cells are then harvested, stained for surface markers (CD3, CD4 and CD8) and fixed. The fixed cells are then permeabilized and stained with anti-cytokine antibodies, washed and analyzed by cytofluorometry.

The results of ICS assays are expressed as the frequency of specific CD4+ T-cells per million total CD4+ T-cells.

PCR Assay for confirmation of suspected cases of HZ

HZ cases will be confirmed by a PCR based algorithm that assesses the presence of VZV DNA in samples, and the adequacy of the samples (by assessing the presence of β -actin DNA).

VZV and β -actin DNA in HZ clinical specimens will be assessed using real-time PCR detection by the 5' nuclease assay based on the Taqman probe technology. If the VZV PCR is negative, β -actin PCR will be performed to assess adequacy of the sample and if a specimen is found to be VZV-PCR negative and β -actin-PCR negative, it is considered to be inadequate.

CONFIDENTIAL

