4.2.2. Main analytical approach

4.2.2.1. Long-term follow-up phase

For persistence of humoral immunity measured after the primary vaccination course, the following parameters will be tabulated. ZOSTER-073 Day 1, study Month 12 and study Month 24 measurements will be displayed in tables and figures in terms of time since primary series in ZOSTER-041, grouped into 1 year intervals.

- GMCs of anti-gE antibody, MGI of post-vaccination timepoint over ZOSTER-041 pre-vaccination timepoint, and anti-gE antibody seropositivity rates with 95% CI;
 - GMCs of anti-gE antibody, MGI of post-vaccination timepoint over ZOSTER-041 pre-vaccination timepoint, and anti-gE antibody seropositivity rates with 95% CI will also be presented with Visit 1, Visit 2, and Visit 3 in the LTFU phase of ZOSTER-073 presented as Day 1, Month 12, and Month 24, in accordance to the primary endpoint timepoints.

- Descriptive statistics on anti-gE antibody concentrations (mean, SD, min, Q1, median, Q3, max);
- Vaccine response rates and 95% CIs to ZOSTER-041 pre-primary vaccination for anti-gE antibody concentrations;
- Descriptive statistics of the fold increase of post-vaccination timepoint over ZOSTER-041 pre-vaccination timepoint at ZOSTER-073 Day 1, study Month 12, and study Month 24 (mean, SD, min, Q1, median, Q3, max);
- Distribution of the fold over ZOSTER-041 pre-vaccination timepoint;
- The distribution of antibody titers will be tabulated and also presented using reverse cumulative curves.

Displays of GMCs of anti-gE antibody concentrations will also include all of the ZOSTER-041 timepoints.

Anti-gE antibody concentrations will be displayed graphically by time since primary vaccination dose 2. Values taken pre-primary vaccination, at 1 month post primary vaccination dose-1, and timepoints post-dose 2 of primary vaccination will be presented in separate symbols and colors in the figure, along with a trend line through post-dose 2 points. A line representing the median pre-vaccination concentration will be displayed for comparison.

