4.2.2.2. Revaccination active phase

For humoral immunity after revaccination for the active phase, the following parameters will be tabulated. ZOSTER-073 study Months 24, 25, and 26 (Visits 3-5), will be presented as pre-revaccination, 1 month post-revaccination Dose 1, and 1 month post-revaccination Dose 2 in displays.

- GMCs of anti-gE antibody and anti-gE antibody seropositivity rates with 95% CI at pre-revaccination, 1 month post-revaccination Dose 1, and 1 month post-revaccination Dose 2;
- Vaccine response rates for anti-gE antibody concentrations at 1 month post-revaccination Dose 1 and 1 month post-revaccination Dose 2 [post-revaccination timepoint over pre-revaccination timepoint] with 95% CI;
- Vaccine response rates to ZOSTER-041 pre-primary vaccination for anti-gE antibody concentrations at 1 month post-revaccination Dose 1 and 1 month post-revaccination Dose 2 with 95% CI;
- MGI post-revaccination timepoint over pre-revaccination timepoint at 1 month post-revaccination Dose 1 and 1 month post-revaccination Dose 2 with 95% CI;
- MGI post-revaccination timepoint over ZOSTER-041 pre-vaccination timepoint at pre-revaccination, 1 month post-revaccination Dose 1, and 1 month post-revaccination Dose 2 with 95% CI;
- Descriptive statistics of the fold increase of anti-gE antibody concentrations 1 month post-revaccination Dose 1 and 1 month post-revaccination Dose 2 over pre-revaccination timepoint (mean, SD, min, Q1, median, Q3, max).

- Distribution of antibody titers at pre-revaccination, 1 month post-revaccination Dose 1, and 1 month post-revaccination Dose 2 will be tabulated and also presented using reverse cumulative curves.
- Boxplots of anti-gE antibody concentrations will be displayed by visit.

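### SAP 4.2.1 defines both anti-gE MGIs on reciprocal concentrations, which read literally is pre over post and conflicts with the protocol and with the SAP's own tabulation instructions

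*SAP*

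**What the plan says.** SAP 4.2.1 gives two MGI definitions, each a geometric mean of within-subject ratios. For the comparison with ZOSTER-041 pre-vaccination, the ratios are "ratios of the post-vaccination reciprocal anti-gE concentration to the Day 0 reciprocal anti-gE concentration". For the comparison with pre-revaccination, they are "ratios of the post-revaccination reciprocal anti-gE concentration to the Month 24 reciprocal anti-gE concentration". SAP 4.3.1.1 sends the reader back to 4.2.1 for the secondary immunogenicity endpoints.

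Protocol 10.3.3 describes the long-term follow-up MGI as the "geometric mean of the ratio post-vaccination timepoint over pre-vaccination timepoint in ZOSTER-041". For the revaccination active phase it asks for "MGI post-revaccination timepoint over pre-revaccination timepoint at Months 25 and 26 with 95% CI".

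The SAP's tabulation sections use the protocol's direction. SAP 4.2.2.1 asks for "MGI of post-vaccination timepoint over ZOSTER-041 pre-vaccination timepoint". SAP 4.2.2.2 asks for "MGI post-revaccination timepoint over pre-revaccination timepoint at 1 month post-revaccination Dose 1 and 1 month post-revaccination Dose 2 with 95% CI". SAP 4.3.1.2.3 words the follow-up phase the same way.

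On the assay, protocol 12.2.1 says that "anti-gE antibody concentrations are calculated from a standard curve", and SAP 4.2.1 adds: "The cut-off for the anti-gE Ab assay is 97 mIU/ml".

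SAP 4.8 lists two departures from the protocol's analyses: the set used for immunogenicity in non-revaccinated subjects, and the period for related SAEs. Neither concerns the MGI.

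**The concern.** A quantity called an increase should exceed 1 when antibody rises. As defined in SAP 4.2.1 it falls below 1. 'Reciprocal' makes sense for a dilution titre, where the reported value is itself the reciprocal of a dilution. Here the result is a concentration read from a standard curve, and taking its reciprocal turns the ratio over.

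The wording sits in the section that defines the endpoints. The MGI summarises the endpoint of both primary objectives and, through the cross-reference in 4.3.1.1, the secondary humoral endpoint in the revaccination follow-up phase. At stake are a reported number that could be the inverse of the one intended, and a SAP that disagrees with the protocol and with itself on a summary of the primary endpoint.

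**Working it through.** The documents give no MGI value, so there is no figure of theirs to reproduce. The check is algebra, a numerical illustration and a comparison of sections.

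**Inputs.** Both definitions and the 97 mIU/ml cut-off come from SAP 4.2.1. The direction comes from protocol 10.3.3 and SAP 4.2.2.1, 4.2.2.2 and 4.3.1.2.3. The 68 subjects are the actual number in SAP Table 1. The SD of 0.4 for the log10 ratio is an assumption, because the documents give none.

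**1. One subject.** Literal SAP 4.2.1: (1/post)/(1/pre) = pre/post. Protocol: post/pre. A subject who rises from 97 to 388 mIU/ml has 388/97 = 4.0 under the protocol and (1/388)/(1/97) = 97/388 = 0.25 under the literal wording. For a rise from 100 to 500 the values are 500/100 = 5 and (1/500)/(1/100) = 0.2.

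| True rise | post/pre | Literal 4.2.1 |
|---|---|---|
| 2-fold | 2 | 0.5 |
| 4-fold | 4 | 0.25 |
| 5-fold | 5 | 0.2 |
| 10-fold | 10 | 0.1 |
| 30-fold | 30 | 0.033 |

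**2. The geometric mean and its interval.** The mean of log10(pre/post) is minus the mean of log10(post/pre), so the literal MGI is exactly 1/MGI. SAP 4.2.1 states the back-transformed Student interval for the GMC; I assume the same method for the MGI. If the limits on the log scale are m ± h, those of the inverse are −m ± h. An interval (L, U) therefore becomes (1/U, 1/L).

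In one simulated sample of 68 subjects (SD of the log10 ratio 0.4), the protocol MGI was 4.99 (95% CI 4.03 to 6.18) and the literal MGI was 0.200 (0.162 to 0.248). Check: 1/4.99 = 0.200, 1/6.18 = 0.162, 1/4.03 = 0.248.

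**3. Agreement with the GMCs.** In the same subjects the ratio of the post GMC to the pre GMC must equal the post/pre MGI. In the simulated sample it was 4.99. The literal 0.200 does not agree with it.

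**4. The sections side by side.**

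| Place | Direction |
|---|---|
| Protocol 10.3.3, follow-up and revaccination phases | post over pre |
| SAP 4.2.2.1 | post over pre |
| SAP 4.2.2.2 | post over pre |
| SAP 4.3.1.2.3 | post over pre |
| SAP 4.2.1, both MGI definitions, read literally | pre over post |

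**5. What is untouched.** The GMC is built on log10 concentrations. Seropositivity compares a concentration with 97 mIU/ml. The vaccine response rate uses a 4-fold rise on direct concentrations. The descriptive fold-increase statistics in SAP 4.2.2.1, 4.2.2.2 and 4.3.1.2.3 are specified as post over pre. None of them depends on the word 'reciprocal'.

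**The case against.** The best defence is that the direction is already settled inside the SAP. Every tabulation instruction says post over pre, and the version history records that version 2.0 added the MGI reference point to 4.2.2.1 in order to clarify it. The definition sentences also name an increase over the earlier value and order the ratio post to pre. The SAP speaks of antibody titres elsewhere for these same concentrations, which suggests loose vocabulary, although the documents do not say where the word came from. An MGI of 0.2 beside rising GMCs and separately tabulated fold increases would be hard to miss. No hypothesis is tested, and the MGI is one of several summaries of the concentration endpoint.

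All of this stands, and it limits the consequence. A reader might infer from 4.2.1 that the SAP plans, or will produce, an inverted MGI. The documents do not support that: the inversion reaches a table only if a programmer follows 4.2.1 literally and passes over 4.2.2 and 4.3.1.2.3. Nor is this a deliberate departure from the protocol, since SAP 4.8 lists none.

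The defence does not make the definition correct. No reading of 'reciprocal' fits a concentration in mIU/ml, and the section that carries the word is the one the SAP points to for definitions.

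**Conclusion.** SAP 4.2.1 is wrong as written for both MGIs. The algebra needs no assumption, and the conflict with protocol 10.3.3 and with the SAP's own instructions can be read off the text. The size is exact but conditional: if 4.2.1 were programmed literally, each MGI would be the inverse of the intended value (0.2 for a 5-fold rise), with the confidence limits inverted and swapped. The simulated interval rests on the assumed SD and on the Student method; the inversion itself rests on neither.

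This is a minor wording correction. The other anti-gE summaries are unaffected, the study is descriptive, and the intended direction is clear from the rest of the plan.

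**What to change.** Delete 'reciprocal' wherever it occurs in the two MGI sentences of SAP 4.2.1. There are four occurrences, two in each sentence. The MGI is then the geometric mean, over subjects, of the post concentration divided by the Day 0 concentration (ZOSTER-041 pre-vaccination) or by the Month 24 concentration (pre-revaccination). Leave those reference timepoints unchanged in this edit. It costs four deleted words and touches no data, sample size or study conduct.

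Do not fold a second change into it by writing 'baseline' for Month 24. SAP 4.1.2 sets the revaccination baseline as the latest non-missing result before revaccination, and the footnote to the revaccination visit table in SAP 1.2 allows Visit 2 or Visit 1 when Visit 3 is unavailable. Month 24 and baseline can therefore differ for a subject who has no Visit 3 result. Whether the MGI should use one or the other is a separate point, to be reconciled explicitly.
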